### 5.10 Number of subjects and statistical power

Sample size is based on prior studies assuming that longer procedure times reflect a need for further dilation and manipulation. Procedure time is defined in this study as first instrument passing into the uterus until last instrument out of the uterus. Previous studies have defined a 3-minute for 14-16 week gestations or 5-minute change for 19-24 week gestations as clinically significant. For this study evaluating 16 - 20 6/7 week gestations, we chose 4-minute difference as clinically significant. Using a superiority design, in order to detect a 4-minute change in procedure time from a baseline of 10 minutes with a standard deviation (SD) 5 minutes), with a two-tailed alpha of 0.05 and power of 90%, 33 women will be needed in each arm. We plan to recruit 72 participants due to post-enrollment exclusion.

### 5.11 Study limitations

While there are many possible regimens of mifepristone and misoprostol, which could be compared, we have tried to select the most reasonable and practical regimen for use in our setting. Additional studies may be needed in the future to compare other regimens. As this study will recruit patients from VCU Medical Center and Virginia League of Planned Parenthood, the study may be generalizable only to patients of similar characteristics. However, since the biologic response to mifepristone and misoprostol is not known to vary significantly, the results should be widely generalizable. Loss of blinding is a concern. Steps have been taken to ensure internal validity in that both participants and practitioners will be blinded to allocation of treatment versus placebo. We will ask both providers and participants which group they believe the participant was in to determine if group assignment was detectable. Limitations of this study will include potential extension of time for recruitment and a relatively small sample size.

### 6. Links with other projects

There is a multicenter trial comparing the addition of mifepristone versus misoprostol to osmotic dilators versus dilators alone.

## 7. Expected outcomes of the study and dissemination of findings

If 20–24 hour mifepristone and 2–4 hour misoprostol produces better cervical dilation than misoprostol only for second trimester D&E's, this regimen could increase the medication only options for surgical procedures. We plan on publishing the study in a reproductive health journal and giving oral presentations of results.

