## 2. Specific Aims

This study aims to compare mifepristone and buccal misoprostol to mifepristone and vaginal misoprostol for cervical preparation for second trimester D&E. We hypothesize that giving oral mifepristone 20-24 hours and vaginal misoprostol 1-2 hours prior to D&E will provide better cervical dilation than mifepristone 20-24 hours and buccal misoprostol 1-2 hours prior to D&E. The primary outcome of the study will be length of procedure as measured by first instrument in the uterus (dilator if further dilation is required or forceps if no further dilation required) to last instrument out of the uterus. Secondary outcomes will include cervical dilation achieved as measured by the largest size Pratt dilator accepted without resistance prior to the start of the procedure, total dilation required, blood loss, pain, complications, provider assessment of difficulty, and provider and patient acceptance and recommendation for other patients.

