## 3. Previous research

The addition of mifepristone, a progesterone antagonist, to a misoprostol regimen has been shown to significantly decrease the medication-to-abortion interval in second-trimester induction terminations. Vaginal administration has demonstrated improved dilation as compared to buccal administration but it is known that patients prefer buccal administration. A comparison of mifepristone and vaginal versus mifepristone and buccal misoprostol has not been studied prior to second-trimester surgical abortion.

A Cochrane review (2010) of cervical preparation for second-trimester D&E did not recommend mifepristone and misoprostol for cervical priming due to high rates of preprocedural expulsions.  However, the primary basis for this conclusion is the trial by Carbonell et al. in which the 48-hour interval between the medications accounts for the high out-of-facility expulsion risk. A retrospective cohort of over 200 women between 14 and 19 6/7 weeks gestation showed no difference in difficulty of cervical dilation for patients receiving mifepristone 24–48 hours misoprostol as compared to osmotic dilators prior to surgical abortion. Two out of facility expulsions occurred in the mifepristone-misoprostol arms but the timing of medication to expulsion interval is not reported.

More recent studies have limited the timing of mifepristone to 24 hours or less prior to procedure. Mifepristone only has been shown to provide adequate cervical dilation as compared to osmotic dilators to 16 weeks gestation with noninferiority design to detect a 3-minute difference in procedure time. A 24-hour interval between 200mg mifepristone and 400mcg buccal misoprostol has been shown as non-inferior to osmotic dilators for total procedure time for 15-18 week surgical abortions. Mifepristone and one-set of osmotic dilators was found to be non-inferior for total procedure time as compared to two sets of osmotic dilators for surgical abortion 19-23 6/7 weeks gestation.

The addition of mifepristone has benefit as a cervical priming agent as an adjunct or alternative to osmotic dilators for surgical abortion, but it is not known whether the addition of vaginal versus buccal misoprostol changes cervical dilation and thus procedure time outcomes.

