### 5. Research design and General Methodological Approach

We have chosen a randomized controlled trial to ensure that neither patient nor provider will be biased by medication choice. Seventy-two English or Spanish-speaking women greater than 18 years of age and at 16 0/7-20 6/7 weeks gestation will be enrolled with 36 women in each arm.

Computer-generated randomization will be utilized to assign treatment arms and the vaginal misoprostol and buccal placebo and buccal misoprostol and vaginal misoprostol will be prepared according to randomization scheme by the research pharmacy in opaque-sealed envelopes as to blind participants and providers.

One arm will receive mifepristone 200mg orally 20–24 hours prior and misoprostol 400mcg (two 200mcg tablets) vaginally 1–2 hours prior and placebo (two lactose tablets designed to appear similar to misoprostol) buccally 1–2 hours prior to D&E. The second arm will receive mifepristone 200mg orally 20–24 hours prior and misoprostol 400mcg (two 200mcg tablets) buccally and placebo (two lactose tablets designed to appear similar to misoprostol) vaginally 1–2 hours prior to surgical abortion. The patients will place the tablets in the pre-operative area from pre-marked envelopes. The patient will be instructed to take the medication in the envelope marked buccally (misoprostol 400 mcg or placebo) to be placed in the cheek pouch for 30 minutes and then remaining swallowed and the envelope marked vaginally (misoprostol 400mcg or placebo) to be placed vaginally as far as the patient can insert with her finger. The patient will be witnessed taking the buccal medication but the patient will be given privacy for vaginal administration. The time will be recorded in the patient's chart. Prior to the procedure, patient assessment of medications will be obtained as detailed in 5.5.

At 1–2 hours after misoprostol and placebo administration, the participant will be brought into a procedure room for a dilation and evacuation (D&E). Prior to the D&E, an assessment of cervical dilation will be made as assessed by largest size Pratt dilator accepted without resistance starting with 39–French. Only the attending will assess cervical dilation but procedures will be performed by the attending and residents-in-training. Type of provider will be recorded.

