### 5.9 Data analysis

STATA statistical software (StataCorp LP, College Station, TX, www.stata.com) will be used to analyze the baseline characteristics of the populations based on the study questionnaires completed by participants prior to their procedure. Primary and secondary outcomes will be recorded as described above in 5.4. Both primary and secondary outcomes will be analyzed using t-tests or appropriate non-parametric comparison tests as appropriate. The perception assessments (VAS) will be assessed using non-parametric analysis. The primary analysis will be based on intention to treat.

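### Does the misoprostol-only comparator in section 7 commit the trial to a conclusion its two arms cannot support?

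*Combined protocol and SAP*

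**What the plan says.** Section 7 opens with a conditional: "If 20–24 hour mifepristone and 2–4 hour misoprostol" "produces better cervical dilation than misoprostol only for second trimester" D&E, then the regimen could widen the medication-only options. Its other sentence says only that the results will go to a journal and to oral presentations.

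Section 5 defines the arms. For the first: "One arm will receive mifepristone 200mg orally 20–24 hours prior and misoprostol 400mcg (two 200mcg tablets) vaginally 1–2 hours prior", with placebo by the buccal route. For the other: "The second arm will receive mifepristone 200mg orally 20–24 hours prior and misoprostol 400mcg (two 200mcg tablets) buccally", with placebo by the vaginal route.

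Section 2 states the hypothesis that the vaginal regimen "will provide better cervical dilation than mifepristone 20-24 hours and buccal misoprostol 1-2 hours prior to D&E", and follows it directly with "The primary outcome of the study will be length of procedure". Cervical dilation is listed there as a secondary outcome. Section 3 links the two by asking whether route "changes cervical dilation and thus procedure time outcomes".

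Section 5.9 says primary and secondary outcomes will be compared by "t-tests or appropriate non-parametric comparison tests as appropriate", with an intention-to-treat primary analysis. Section 5.10 gives a superiority calculation for a 4-minute difference in procedure time: SD 5, two-sided 0.05, 90% power, 33 per arm.

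**The concern.** A section on expected outcomes and dissemination should describe what the trial can find. This one names a contrast, mifepristone plus misoprostol against misoprostol alone, that neither arm supplies. Taken literally, it promises evidence on adding mifepristone, and no result from these arms could give that.

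Three further points seem to add weight:

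- The same sentence departs from the rest of the protocol on misoprostol timing.
- The only hypothesis in section 2 concerns dilation, while the powered endpoint is procedure time.
- Section 5.9 names tests but no effect estimate or confidence interval, so a non-significant p-value might be reported as showing that route does not matter.

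Together these could suggest a trial unsure of its question. If that were so, the published conclusion could be one the data do not support.

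**Working it through.** **1. The passages side by side.**

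| Element | Section 7 | Rest of the protocol |
|---|---|---|
| Comparator | Misoprostol alone | Mifepristone plus buccal misoprostol (abstract, sections 2, 4, 5) |
| Factor that differs | Mifepristone | Misoprostol route (abstract, sections 2, 4, 5) |
| Outcome named | Cervical dilation | Procedure time primary, dilation secondary (abstract, section 2) |
| Misoprostol interval | 2–4 hours | 1–2 hours (abstract, sections 2, 5) |

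The comparator and the interval conflict with the rest of the protocol. Naming dilation does not, because it is the hypothesis in section 2 and a prespecified secondary outcome.

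**2. Does anything depend on section 7?** Allocation is in section 5.2, treatment in section 5, the outcomes in sections 2 and 5, the tests in section 5.9 and the sample size in section 5.10. None refers to section 7. Section 5 also has the interval from misoprostol to the assessment of dilation recorded for each participant, so the interval actually used will be known.

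**3. Which comparison is the trial powered for?** Inputs from section 5.10: difference 4 min, SD 5 min, two-sided alpha 0.05, power 90%.

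n per arm = 2 × (1.960 + 1.282)² × (5/4)² = 2 × 10.51 × 1.5625 = 32.8, so 33.

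The stated figure reproduces. Power from the t distribution is 89.3% at 33 per arm and 91.7% if all 36 are analysed. A one-sided alpha of 0.05 would give 27, so the stated two-sided basis is the one used. The calculation is for a difference in procedure time between the two randomised arms, which differ by route.

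**4. The hypothesis in section 2.** Procedure time is named as primary in the very next sentence. Section 3 runs from dilation to procedure time, and section 5.10 states the assumption that longer procedures reflect a need for more dilation. The mechanism and the endpoint are both disclosed, so the order of the sentences is a matter of labelling.

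**5. The missing interval.** The 95% half-width at SD 5 is:

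- 33 per arm: t(0.975, 64) × 5 × √(2/33) = 1.998 × 1.231 = 2.46 min
- 36 per arm: t(0.975, 70) × 5 × √(2/36) = 1.994 × 1.179 = 2.35 min

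With 33 per arm, an observed difference below 2.46 min is non-significant, and one above 4 − 2.46 = 1.54 min has an interval that reaches 4. A non-significant result can therefore leave the 4-minute difference open, and an interval would show it. The t-test is built from the difference in means and its standard error, so the interval needs nothing further. A rank test would need one more step, such as a Hodges-Lehmann shift with its interval.

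**The case for a change.** The strongest reply is that a condition the trial can never test is a real misstatement, whatever its place in the document. The sentence conflicts with the protocol on two counts, comparator and timing. Section 5.9 is the whole analysis plan, and it is silent on estimation in a trial that section 5.11 itself calls relatively small. Suppose the true difference were 2 min, which is an assumption. By simulation with SD 5 and 33 per arm, 64% of trials would be non-significant, and 28% of all trials would be non-significant with an interval still reaching 4 min.

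Part of this stands. The sentence is wrong, and the two intervals must be reconciled. Reporting the difference in procedure time with its 95% interval is good practice.

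The rest does not carry. The 28% depends on assumed values: it runs from 4% at SD 4 to 66% at SD 7. It also has no bearing on the comparator. No section says that a non-significant result will be read as equivalence.

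A rule barring no-difference wording while the interval includes 4 min would imply that such wording is allowed once the interval excludes 4 min. That brings a 4-minute equivalence margin into a superiority trial. Under the same assumptions, 1 − 0.283/0.640 = 56% of non-significant trials would fall under that permission despite a real 2-minute difference.

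**Conclusion.** No change to the plan follows. Section 7 contains a clerical slip in one conditional sentence, and the documents settle the intended comparison elsewhere. Correcting it would leave the arms, the primary outcome, the tests, the 33 per arm and the 72 recruited exactly as they are. The 2–4 hour and 1–2 hour statements contradict each other and must be reconciled by the sponsor. Nothing here says which is right, and no statistical quantity in the plan depends on it.

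The hypothesis in section 2 is adequately tied to the primary outcome. The missing estimate and interval in section 5.9 are a detail that an analyst comparing two means would ordinarily supply from the same output.

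This rests on two assumptions: that the arms are delivered as section 5 defines them, and that the procedure-time difference is reported with its interval. If a rank test is used, the second assumption takes a deliberate extra step, but that is reporting advice and needs no change of design or analysis.

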## 8. Budget justification

## 8.1. Personnel

Principal investigator: [name] will assist in subject recruitment, obtaining consent, data analysis, dissemination of findings, and performing procedures related to data acquisition. The following physicians will also assist in subject recruitment and obtaining consent: [name]. The research coordinator will be a paid position. He/she will assist in subject recruitment, obtaining consent, treatment allocation and concealment. We anticipate supplementing an existing research coordinator for approximately \$5,755 with 34.3% fringe. Please see attached budget document for further details.

### 8.2. Equipment

We anticipate utilizing the ultrasound machine and computers currently available at the study sites.

# 8.3. Materials and Supplies

These include the cost of the medication and placebo, concealment for misoprostol and placebo, envelopes. The total is \$7,161

### **8.4. Participant Incentives**

Each participant will receive a \$10 Target gift card as reimbursement for time after completion of the study, approximately \$720.

# 8.5. Travel

No travel reimbursement required.

### 9. Timeline

Recruitment will begin July 2015 and extend for approximately 9-months or once enrollment is complete. As recruitment will occur on patient's initial consultation for procedure and allocation and assessment will occur on the day of procedure, data collection will be complete the day of the patient's procedure. Data analysis will follow and will complete prior to the writing of the final report-please see timeline attached.

